10.2 SAMPLE SIZE DETERMINATION

The primary endpoints of this trial are to 1) identify the MTD and the desirable dose of the tofacitinib + LMB-100 combination format and 2) to determine whether the combination results in 80% of patients achieving threshold drug levels during cycle 2 of LMB-100. The MTD is defined as the maximum dose at which less than 33% of patients experience a DLT. The desirable dose will be selected from among the dose levels at or below the MTD. A lower dose than the MTD might be assessed in the expansion phase if chronic toxicity of LMB-100 is judged to be intolerable by the investigator at the MTD.

As per standard 3+3 design, if 0 of 3 or <2 of 6 patients experience DLT then dose escalation may proceed. If 2 or more patients experience DLT at any dose level, then dose de-escalation is required.

Dose escalation will proceed from dose level 1 to 2. If 0 of 3 or 0-1 of the first 6 patients in dose level 1 have a DLT, then dose escalation will proceed to dose level 2. Alternatively, if 2 or more patients in level 1 experience DLT, then dose will be de-escalated to dose level -1.

Based on two dose levels, the theoretical maximum number of subjects that can enroll on the dose escalation would be 12 (6 patients per level x2 dose levels).

Following completion of the dose escalation, enrollment of an additional 15 patients with pancreatic cancer or extrahepatic cholangiocarcinoma will be undertaken to better assess the a) safety of the optimal dose in the target population, and b) ability of tofacitinib to delay development of ADAs against LMB-100 and result in serum LMB-100 drug levels reaching threshold in cycle 2 and beyond. Participants on the dose escalation arm who are treated at MTD and meet eligibility requirements for the dose expansion phase can be counted towards the 15 patients needed to accrue to the expansion phase. We estimate that as many as 50% of patients

who start treatment will develop progressive disease by restaging after 2 cycles and would therefore be uninformative for assessing the longer-term immunogenicity endpoint. Thus, additional patients may be needed to complete the evaluation of toxicity and possible efficacy at the escalating dose levels.

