This evaluation in 15 patients of either histology (but at least 8 patients in this expansion phase must have pancreatic adenocarcinoma) will be undertaken using the following guidelines: The objective will be to determine if the fraction of patients who are able to achieve threshold levels of LMB-100 in cycle 2 is consistent with 80% and greater than 50%. If 15 evaluable patients are enrolled, and if 11 or more patients meet threshold drug levels in cycle 2, then the probability of this occurring is 5.9% if the true probability of achieving threshold drug levels in cycle 2 were 50% and the probability of this occurring is 83.6% if the true probability of achieving threshold drug levels in cycle 2 were 80%. Thus, the expansion phase would be considered to have a positive outcome if 11 or more of 15 patients in the expansion phase achieve threshold drug levels. In practice, after the trial has ended accrual, the fraction of evaluable patients assessed during the expansion phase that achieve threshold drug levels in cycle 2 will be determined and reported along with two-sided 80% and 95% confidence intervals to aid in interpretation of the results. The fraction of patients who achieve threshold drug levels in cycle 3 will also be reported along with a 95% confidence interval, but this may be a small fraction and will be interpreted as being an exploratory evaluation.

As an early stopping rule, if after the first 5 evaluable patients in the expansion cohort have been treated, 0 of the 5 achieve threshold drug levels in cycle 2, then no further patients will be accrued as soon as that can be determined, with no pause in accrual, since this would be inconsistent with the goal of having 11 or more of 15 patients achieving threshold drug levels in cycle 2.

With up to 12 patients in the dose escalation phase and 15 in the expansion cohort, a maximum of 27 evaluable patients are required to complete accrual to this study. The accrual ceiling will be set at 45 patients to account for screen failures or patients who are treated but unable to complete the DLT period. It is anticipated that up to two patients per month may enroll onto this trial. Thus, accrual is expected be completed in approximately 2 years.

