10.3 POPULATIONS FOR ANALYSES

10.3.1 Evaluable for toxicity

All patients who receive treatment during dose escalation will be reported. Any patient who receives any study drug treatment and experiences a DLT related to study drug within 21 days of initial treatment is evaluable. Otherwise, patients evaluable for DLT must: 1) receive all doses of study drugs, 2) be followed for study drug toxicity for at least 21 days after the administration of the first dose of LMB-100.

In the expansion phase, up to 15 evaluable patients who can have their drug levels assessed in cycle 2 will be included in analyses. Up to 5 patients will be replaced if they have PD before C2, but if more than 5 patients progress before C2, then no further patients will be accrued as soon as this can be determined.

10.3.2 Evaluable for objective response:

Only those patients who have measurable disease present at baseline, have received at least one cycle of therapy, and have had their disease re-evaluated will be considered evaluable for response. These patients will have their response classified according to the definitions stated below. (Note: Patients who exhibit objective disease progression prior to the end of cycle 1 will also be considered evaluable.) Responses or progressions noted in patients receiving treatment extension will be recorded in the study database but will not be reported in the aggregate objective response rate, which only corresponds to assessments taken prior to the start of a 4th cycle.

10.3.3 Evaluable Non-Target Disease Response:

Patients who have lesions or tumor marker present at baseline that are evaluable but do not meet the definitions of measurable disease, have received at least one cycle of therapy, and have had their disease re-evaluated will be considered evaluable for non-target disease. The response assessment is based on the presence, absence, or unequivocal progression of the lesions or increase in tumor marker.

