10.4.3 Analysis of the Secondary Endpoint(s)

The secondary endpoints are the number and description of adverse events by grade in the expansion cohort. For both dose escalation and expansion cohorts secondary endpoints include: the LMB-100 peak serum level and half-life and AUC during cycle 1. Each of these will be reported using descriptive measures such as percentages and counts as appropriate. For both dose escalation and dose expansion cohorts, we will report the percentage of patients who have formation of neutralizing anti-LMB-100 ADAs affecting drug concentration during cycle 2 and cycle 3.

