10.4.4 Safety Analyses

Safety will be evaluated during the dose escalation phase and will include reporting toxicities by grade and type at each dose level in addition to DLTs.

During the 15-patient expansion cohort, the following rule will be used: Within the initial 6 patients, no more than 1 patient in 6 is permitted to experience a DLT attributable to study agents. After the initial 6 patients, safety will be monitored continuously per the following rule: if the cumulative fraction of patients enrolled who experience a DLT attributable to study agents is 1/6 or less, patients will be allowed to continue to enroll onto this protocol.

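### The plan defines no all-treated safety population for the expansion phase, and its expansion DLT rule divides by patients enrolled rather than patients assessed for DLT

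*Combined protocol and SAP*

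**What the plan says.** **Population.** Section 10.3.1 (Evaluable for toxicity) opens with "All patients who receive treatment during dose escalation will be reported". It then says: "Any patient who receives any study drug treatment and experiences a DLT related to study drug within 21 days of initial treatment is evaluable". Other patients are DLT-evaluable only if they receive all doses of the study drugs and are followed for at least 21 days after the first LMB-100 dose. For the expansion phase it says only that as many as 15 evaluable patients "who can have their drug levels assessed in cycle 2 will be included in analyses", with up to five replacements for progression before cycle 2.

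**Safety endpoint.** Section 10.4.3: "The secondary endpoints are the number and description of adverse events by grade in the expansion cohort". Section 10.1.2 lists the same endpoint. Neither names a denominator.

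**Safety rule.** Section 10.4.4 allows at most one DLT in the first six expansion patients. After that, accrual may continue "if the cumulative fraction of patients enrolled who experience a DLT attributable to study agents is 1/6 or less".

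**Related figures.** Section 10.2: "The MTD is defined as the maximum dose at which less than 33% of patients experience a DLT". Table 9 accepts at most 1 DLT in 6. Section 10.2 also lets eligible escalation patients treated at the MTD count toward the 15, without saying whether their DLTs enter the 10.4.4 rule. It gives the chance of 11 or more successes in 15 as 5.9% at a true rate of 50%; at 80%, "the probability of this occurring is 83.6% if the true probability of achieving threshold drug levels in cycle 2 were 80"%. No operating characteristics are given for the safety rule.

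**The concern.** A cycle 2 drug level exists only for someone who reached cycle 2. If that condition carries over to the adverse event tables, they describe patients selected partly for having tolerated cycle 1, and toxicity is understated. Safety in pancreatobiliary cancer is a stated secondary objective of the expansion (section 1.1.2).

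The monitoring rule has a different weakness. A patient enrolled but not yet observed adds one to the denominator and cannot yet add to the numerator. The same DLT data can therefore support opposite accrual decisions, depending on how many patients have just been enrolled.

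**Working it through.** **1. Who falls outside the expansion sets.** Take a patient who leaves during or after cycle 1 without a cycle 2 level.

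- *With a drug-related DLT:* evaluable under 10.3.1, in a sentence not limited to escalation. Section 3.1.1 also makes it a DLT if drug-related events prevent cycle 2 from starting within two weeks.
- *With an infusion reaction up to grade 3:* exempt from DLT status (3.1.1), yet a grade 3 reaction despite steroid premedication ends study therapy (3.2.2.4.1). The exemption and the cycle 2 start clause are not reconciled for this patient.
- *With grade 2 renal toxicity that does not recover within 48 hours:* no more LMB-100 that cycle (Table 12). Grade 2 is below the general grade 3 DLT threshold. The patient has not received all doses, so is not DLT-evaluable, and is in neither set if cycle 2 is never reached.
- *Replaced for progression before cycle 2:* no cycle 2 level. Any cycle 1 toxicity short of a DLT is in neither expansion table set.

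Size of the last group, if all five replacements are used: 15 + 5 = 20 treated, and 5/20 = 25% are outside the set.

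**2. The denominator.** The limit is 1/6 = 16.7%.

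- 11 patients assessed, 2 DLTs: 2/11 = 18.2%, above the limit.
- Enrol a twelfth, not yet assessed: 2/12 = 16.7%, within the limit.

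No new safety information has arrived between these two lines.

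**3. The plan's own figures.** With X ~ Bin(15, p):

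- p = 0.5: P(X ≥ 11) = (1365 + 455 + 105 + 15 + 1)/32768 = 1941/32768 = 5.92% (stated 5.9%).
- p = 0.8: P(X ≥ 11) = 83.58% (stated 83.6%).

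Both reproduce.

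**4. How often the 1/6 rule halts.** The documents give no true DLT rate p, so it is an assumption. Assume also independent patients, immediate outcomes and no carried-in patients. The rule allows at most 1 DLT through patient 11 and at most 2 for patients 12 to 15. The chance of passing every look through patient 14 is

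P(continue) = P(X₁₁ = 0)·P(Y₃ ≤ 2) + P(X₁₁ = 1)·P(Y₃ ≤ 1),

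with X₁₁ ~ Bin(11, p) and Y₃ ~ Bin(3, p).

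| True DLT rate | P(continue) | Halt before patient 15 |
|---|---|---|
| 5% | 0.5688×0.9999 + 0.3293×0.9928 = 0.896 | 10% |
| 10% | 0.3138×0.9990 + 0.3835×0.9720 = 0.686 | 31% |
| 16.7% | 0.1346×0.9954 + 0.2961×0.9259 = 0.408 | 59% |
| 20% | 0.0859×0.9920 + 0.2362×0.8960 = 0.297 | 70% |

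The halt probability passes 50% at a true rate of about 14%.

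**5. Effect of the choices left open.**

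- *Pending patients.* With one patient always enrolled but unassessed, the second DLT is tolerated from the 11th assessed patient instead of the 12th, so 10 replaces 11 in the formula. At 16.7%: 0.1615×0.9954 + 0.3230×0.9259 = 0.460, a halt probability of 54% against 59%.
- *Carried-in patients.* At a true rate of 20%, halting by patient 15 is 72% with none carried in, 35% with six DLT-free MTD patients carried in, and 73% with six carrying one DLT.

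**The case against.** The cycle 2 sentence speaks of drug levels and of replacement for progression, so its natural subject is the primary endpoint. Section 6.1 records adverse events from Study Day 1, and section 10.4.3 attaches no cycle 2 condition to the expansion tables. A sensible analyst would probably tabulate everyone treated. That is fair, but the sentence sits under the toxicity heading, the all-treated sentence beside it names escalation only, and no other section supplies the denominator.

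A reader might go further and infer that all cycle 1 toxicity drop-outs disappear. The documents do not support that. Section 10.3.1 keeps any treated patient with a drug-related DLT evaluable, and section 3.1.1 makes most drug-related failures to reach cycle 2 DLTs. The group at risk of omission is patients with toxicity short of a DLT, and it may be small.

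A reader might also infer that the 1/6 rule is wrong because it would probably halt a dose meeting the 33% definition. That holds only for assumed true DLT rates above about 14%, with no patients carried in. The 1/6 limit matches Table 9, and a conservative safety bound may be intended. Nor does a toxicity halt make the 83.6% wrong: section 10.2 states it for 15 evaluable patients, and the observed fraction is to be reported with confidence intervals.

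**Conclusion.** The concern holds as two gaps in wording, each with a practical consequence.

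- The expansion phase has no stated all-treated safety population. Taken literally, its adverse event tables omit cycle 1 leavers with toxicity that is not a DLT. How many is unknown; replaced progressors alone could put up to 25% of treated patients outside the set.
- The enrolled-patient denominator conflicts with the DLT-evaluable definition in 10.3.1 and can reverse an accrual decision on identical data (2/11 against 2/12). Under the assumptions above, one pending patient lowers the halt probability at a 16.7% DLT rate from 59% to 54%.

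The treatment of carried-in escalation patients matters more (35% against 73% at a 20% rate) and is not specified. The section 10.2 definition of the MTD and the 1/6 criterion in Table 9 and section 10.4.4 need to be reconciled; which limit is right is not a matter for this review.

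**What to change.** 1. In 10.3.1, state that the cycle 2 set applies only to the drug-level endpoint. Add an expansion safety population of all patients who receive any dose of tofacitinib or LMB-100, and use it for every expansion adverse event table.
2. In 10.4.4, compute the DLT fraction over DLT-evaluable patients: those with a DLT, plus those who have completed the DLT window as 10.3.1 requires. Say whether escalation patients counted toward the 15 enter both numerator and denominator.
3. Optionally, report the rule's halting probabilities over a range of assumed DLT rates, and align the MTD wording in 10.2 with Table 9 and 10.4.4.

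The cost is protocol wording only: no extra patients, visits or samples. The one drawback is that the rule may trigger slightly earlier, because pending patients no longer dilute the fraction.

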1.2 BACKGROUND AND RATIONALE

1.2.1 Background on disease

Pancreatic cancer is the fourth most common cause of cancer death in the United States, claiming more than 40,000 lives each year. Incidence nearly equals mortality with just 6% of patients living five years beyond their diagnosis. Most patients are diagnosed at an advanced stage, but even patients with early stage disease have a long term survival of less than 20%.(1) Combination chemotherapy with FOLFIRINOX provides the greatest survival advantage for patients who have advanced disease, but the median overall survival (OS) for this regimen does not reach one year and most pancreatic cancer patients are not fit enough to tolerate it.(2) Gemcitabine with NABpaclitaxel is an alternative regimen and extends median overall survival to 8.5 months from 6.7 months with gemcitabine alone. The response rate (RR) to this regimen in the first-line is 23% with less than 1% of patients achieving a complete response (CR).(3) Prospective and retrospective cohort studies have estimated a 17% RR to this regimen when given in second-line to good performance status patients following FOLFIRINOX.(4,5) Single agent gemcitabine remains the recommended treatment for patients with poor performance status. Erlotinib is the only targeted therapy with efficacy against this disease and extends median OS by approximately 10 days when added to gemcitabine at the expense of significant toxicity.(6) Median survival of patients able to receive second line therapy is approximately 3-6 months.(7) New paradigms for the effective treatment of pancreatic cancer are sorely needed.

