Procedure	Screening	Day 1	Day 3*	Day 4	Day 6	Day 8	Day 9	Day 15	Day 21	Safety Follow Up Visit ⁷	Long Term Follow Up ¹¹
PKs		Please refer to Section 5.2									
Correlative Studies		Please	refer to Sec	ction 5.2							
Annual phone call to monitor survival and additional CA therapy											Х
Adverse events ¹⁰		Monitored continuously									
Concomitant meds		Monitored continuously									

*If not performed on day 3, may be performed on day 4 prior to the start of LMB-100 infusion

- Vital signs including temperature, blood pressure, pulse rate, and oxygen saturation should be recorded on the indicated days. In addition, systolic blood pressure, pulse rate, and oxygen saturation must be monitored pre-infusion, every 15 minutes (± 5 minutes) during the infusion, at end of infusion (EOI), then 30, 60 and 120 minutes (±15 minutes) following EOI.
- ² CBC with differential, Acute Care Panel, Hepatic Panel, Mineral Panel, C-reactive protein (CRP), Creatine Kinase (CK), PT, PTT, LDH. PT and PTT will be done only at the time of screening, Day 1 of each cycle, and within 24hrs prior to biopsies (if biopsy will be performed).
- ³ Pregnancy test required in women of childbearing potential; i.e. premenopausal women and women ≤ 2 years after menopause (menopause is defined as amenorrhea for > 2 years)
- ⁴ Assessment may occur at any time prior to enrollment
- ⁵ Applicable only to patients on dose escalation with tumor types other than pancreatic adenocarcinoma, extrahepatic cholangiocarcinoma, or epithelioid subtype of mesothelioma
- ⁶ As indicated in Section **11.3**, all subjects will be offered the opportunity to complete an NIH advanced directives form. This should be done preferably prior to beginning treatment but can be done at any time during the study as long as the capacity to do so is retained. The completion of the form is strongly recommended but is not required.
- ⁷ Safety follow up will occur 3 6 weeks after last dose of study therapy. If the patient is unable to return to the clinic for the follow up visit, an adverse event assessment will be performed by telephone.

- ⁸ Scans, every ~9 weeks, will only be performed until disease progression. Note: for patients on long term follow up, scans may be performed outside of NIH. Gadolinium will be used for MRI in patients where MRI is required.

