6.3.3.3 Evaluation of Best Overall Response

The best overall response is the best response recorded from the start of the treatment until disease progression/recurrence (taking as reference for progressive disease the smallest measurements recorded since the treatment started). The patient's best response assignment will depend on the achievement of both measurement and confirmation criteria.

Target Lesions	Non-Target Lesions	New Lesions	Overall Response	Best Overall Response when Confirmation is Required*
CR	CR	No	CR	≥4 wks. Confirmation**
CR	Non- CR/Non-PD	No	PR	
CR	Not evaluated	No	PR	>4 wks. Confirmation**
PR	Non- CR/Non- PD/not evaluated	No	PR	
SD	Non- CR/Non- PD/not evaluated	No	SD	Documented at least once ≥4 wks. from baseline**
PD	Any	Yes or No	PD	
Any	PD***	Yes or No	PD	no prior SD, PR or CR
Any	Any	Yes	PD	

For Patients with Measurable Disease	(i.e., Target Disease)
--------------------------------------	------------------------

new lesion.

** Only for non-randomized trials with response as primary endpoint.

In exceptional circumstances, unequivocal progression in non-target *** lesions may be accepted as disease progression.

Note: Patients with a global deterioration of health status requiring discontinuation of treatment without objective evidence of disease progression at that time should be reported as "symptomatic deterioration." Every effort should be made to document the objective progression even after discontinuation of treatment.

New Lesions	Overall Response	
No	CR	
No	Non-CR/non-PD*	
No	not evaluated	
Yes or No	PD	
Yes	PD	
	No No No Yes or No	

For Patients with Non-Measurable Disease (i.e., Non-Target Disease)

* 'Non-CR/non-PD' is preferred over 'stable disease' for non-target disease since SD is increasingly used as an endpoint for assessment of efficacy in some trials so to assign this category when no lesions can be measured is not advised

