6.3.6 Objective Response Rate

Objective response rate (ORR) is defined as the proportion of patients with partial response or complete response.

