6.3.7 Disease Control Rate

Disease control rate (DCR) is defined as the percentage of patients with partial response, complete response, or stable disease.

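### Section 10.3.2 drops treated patients with no re-evaluation from the ORR denominator instead of counting them as non-responders, and the 9-week DCR has no stated denominator

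*Combined protocol and SAP*

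**What the plan says.** All places are in the combined protocol and SAP.

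- **Response set (Section 10.3.2).** It is limited to patients with measurable disease at baseline who "have received at least one cycle of therapy, and have had their disease re-evaluated will be considered evaluable for response". A note adds one group: "Patients who exhibit objective disease progression prior to the end of cycle 1 will also be considered evaluable". The same paragraph ties the set to ORR: responses seen during treatment extension "will not be reported in the aggregate objective response rate, which only corresponds to assessments taken prior to the start of a 4th cycle".
- **Endpoint definitions.** Section 6.3.6: "Objective response rate (ORR) is defined as the proportion of patients with partial response or complete response". Section 6.3.7: "Disease control rate (DCR) is defined as the percentage of patients with partial response, complete response, or stable disease". Neither names an analysis set. Section 10.4.9 plans the 9-week DCR with a 95% confidence interval in the expansion cohort, again without a denominator.
- **Clinical decline (Section 6.3.3.3).** The label used is symptomatic deterioration: "Patients with a global deterioration of health status requiring discontinuation of treatment without objective evidence of disease progression at that time should be reported as". Nothing maps that label, or death before a scan, to non-response.
- **Timing.** Footnote 8 of the Study Calendar (Section 3.4): "Scans, every ~9 weeks, will only be performed until disease progression". Section 6.3 instead asks for response re-evaluation every 6 weeks.
- **Prognosis (Section 1.2.1, pancreatic cancer).** "Median survival of patients able to receive second line therapy is approximately 3-6 months".
- **Status of the endpoints.** Section 1.1.3 lists ORR and DCR as exploratory.

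**The concern.** A patient who starts treatment and dies or declines before any re-evaluation is a treatment failure. Sections 6.3.5 and 6.3.8 treat a death that way for PFS and OS, which run from start of treatment. In ORR the same patient disappears from the denominator. Such patients are almost never responders, so leaving them out can in practice only raise the rate.

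ORR and DCR are the plan's preliminary look at activity, and a reader will take them as rates among treated patients. In a cohort of about 15, a few missing failures move a percentage visibly. For DCR the first problem is that the denominator is undefined. Section 10.3.2 says the evaluable patients are the ones whose response is classified, so using that set for DCR is a natural choice, but it is not a stated rule.

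**Working it through.** **1. The plan's own figure.** The only operating characteristics given are for the expansion rule of at least 11 of 15 (Section 10.2). Exact binomial:

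- p = 0.50: (1365 + 455 + 105 + 15 + 1)/32768 = 1941/32768 = 0.0592 (stated 5.9%)
- p = 0.80: 0.8358 (stated 83.6%)

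Both reproduce. They concern cycle 2 drug levels and do not use the Section 10.3.2 set. No target or power is stated for ORR or DCR.

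**2. Who is in the ORR denominator** (treated, measurable disease at baseline):

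| Course | In the set? |
|---|---|
| At least one cycle, any re-evaluation | Yes |
| Objective progression before end of cycle 1 | Yes, by the note |
| At least one cycle, then death, decline or withdrawal with no re-evaluation | No |
| Less than one cycle, no objective progression documented | No |

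**3. Size in general.** Let N be treated patients with measurable disease, k those dropped (none a responder), x responders, and d = k/N. The reported rate is x/(N-k), and the all-treated rate is x/N. Their ratio is N/(N-k) = 1/(1-d):

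- d = 0: 1.00
- d = 10%: 1/0.90 = 1.11
- d = 20%: 1/0.80 = 1.25

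**4. Illustration with N = 15.** The values of k and x are assumptions. The DCR column applies only if DCR uses the same set.

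| Dropped k | ORR, 1 responder | ORR, 2 responders | DCR, 7 controlled |
|---|---|---|---|
| 0 (all-treated value) | 6.7% | 13.3% | 46.7% |
| 1 | 7.1% | 14.3% | 50.0% |
| 3 | 8.3% | 16.7% | 58.3% |
| 5 | 10.0% | 20.0% | 70.0% |

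Exact 95% intervals for the all-treated values are 1.7-40.5% for 2/15 and 21.3-73.4% for 7/15.

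**5. Upper bound on exclusion by death.** Assume exponential survival with median m = 3 or 6 months (Section 1.2.1) and 4.345 weeks per month. The share dead by time t is 1 - 0.5^(t/m).

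| First scan | t (months) | m = 6 | m = 3 | Of 15 | 1/(1-d) if every death were an exclusion |
|---|---|---|---|---|---|
| Week 6 | 6/4.345 = 1.381 | 0.147 | 0.273 | 2.2 to 4.1 | 1.17 to 1.38 |
| Week 9 | 9/4.345 = 2.071 | 0.213 | 0.380 | 3.2 to 5.7 | 1.27 to 1.61 |

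Some of these patients would have documented progression or an earlier scan before death and would stay in the set, so the figures bound exclusion by death from above. Decline or withdrawal without a scan would come on top.

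**6. If the 15 are those with cycle 2 drug levels** (Section 10.3.1), each has reached about study day 25, which is 24 days or 3.43 weeks after the start. From there:

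- to week 6: 2.57 weeks = 0.592 months, giving 0.066 (m = 6) to 0.128 (m = 3), or about 7-13%
- to week 9: 5.57 weeks = 1.282 months, giving 0.138 to 0.256, or about 14-26%

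**The case against.** The strongest reply is that few patients need go unassessed. Section 10.3.2 asks that disease was re-evaluated. It does not ask for a scan at week 9. The Study Calendar marks imaging at the safety follow-up visit, 3-6 weeks after the last dose, and Section 3.5 asks for effort to have every subject complete that visit. Patients who stop for reasons other than progression are invited back about every 6 weeks for scans. Section 6.3.3.3 asks for every effort to document objective progression after discontinuation. This stands and narrows the gap mainly to death or refusal with no scan, and to stopping within cycle 1 without objective progression. It does not close the gap: footnote 7 of the calendar replaces the visit by a telephone adverse event check when the patient cannot return, and footnote 11 makes later visits optional.

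A second reply is that little hangs on it. Both endpoints are exploratory, PFS and OS count the deaths, and the effect on ORR is small. Section 1.2.8.2.2 reports 1 response in 14 patients for LMB-100 with nab-paclitaxel at its MTD. With 1 responder here and 3 patients dropped, ORR moves from 6.7% to 8.3%, well inside the confidence interval. This also stands, and it sets the severity.

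A reader might infer three stronger points that the documents do not support:

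- **Everyone who dies or stops before week 9 is dropped.** An earlier re-evaluation, or objective progression before the end of cycle 1, keeps the patient in.
- **The plan inflates DCR.** No set is assigned to DCR.
- **The rates are inflated 1.3 to 1.6 fold.** That takes every death before week 9 as an unscanned exclusion, uses only the longer of two scan intervals, and applies a second-line pancreatic cancer median to a cohort that also admits extrahepatic cholangiocarcinoma.

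**Conclusion.** The point holds for ORR. Section 10.3.2 takes out of the denominator any treated patient with measurable disease who has no re-evaluation or did not receive one cycle, unless objective progression was documented before the end of cycle 1. Death, symptomatic deterioration or withdrawal with no scan is then not counted as non-response, and the bias is upward. For the 9-week DCR, the finding is an unstated denominator, with the same bias if the response-evaluable set is used.

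The documents do not give the size. It is 1/(1-d) for a dropped share d, and nil if every patient is re-evaluated or has early objective progression. The 15-27% (week 6) and 21-38% (week 9) figures rest on exponential survival and the quoted 3-6 month median, and they are upper bounds on exclusion by death. Severity is low: no primary decision rule uses this set.

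**What to change.** - In Sections 10.3.2 and 10.4.9, report ORR and 9-week DCR over all treated patients with measurable disease at baseline. Section 2.1.1.3 already requires measurable disease of every expansion patient.
- Count patients with no post-baseline assessment because of death, symptomatic deterioration or withdrawal as not responding and not controlled, and report how many there are by reason.
- Name this denominator for DCR in Sections 6.3.7 and 10.4.9.
- Keep the evaluable-set figures as supportive.
- Reconcile the 6-week interval in Section 6.3 with the roughly 9-week interval in footnote 8 of the Study Calendar, because a later first scan lengthens the time in which a patient can be lost unassessed.

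The cost is wording only, since treatment start and baseline measurability are already recorded. The reported exploratory rates become somewhat less favourable. The sample size and the 11-of-15 rule do not change.
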